Care. The investigators will be responsible for alerting the sponsor to any event that seems unusual, even if the event may be considered an unanticipated benefit to the subject. By exercising appropriate health-care options, the investigator remains responsible for managing AEs that are serious or that cause the subject to discontinue before completing the study. Frequency of follow-up beyond that mandated in the protocol is left to the discretion of the investigator.

Confidentiality and HIPAA considerations

All subjects must provide written informed consent and signed HIPAA authorization prior to the performance of any screening or main study procedures. Subject confidentiality will be protected throughout the study and no subject-identifying information will be released to anyone outside the project. Confidentiality will be secured through several mechanisms. Each subject will be assigned an anonymous study ID, which will be used on all study forms. Any study forms and paper records containing personal identifier information (e.g., address, phone number) will be kept secured and locked at each clinical site. No personal identifiers will be placed on biological samples and other documents forwarded to central labs and reading centers.

Access to all subject data and information at the clinical sites, including biological samples, will be restricted to authorized personnel. Only authorized personnel at the coordinating center will have access to study data files. Authorized personnel will be assigned user logon IDs, passwords and appropriate access privileges to study data. Study subjects will be identified only by their initials and subject ID number. No personal identifiers such as name, address, social security number will be entered into the study database. Any subject-specific data reported to any study committees will only be identified by subject ID number.

Finally, subjects will not be identified by name in any reports or publications, nor will the data be presented in such a way that the identity of individual subjects can be inferred. Analysis files created for further study by the scientific community will have no subject identifiers.

Protection against subject risks related to the study medication

Subjects will be provided with written, detailed instruction for calling the study coordinator or physician, including but not limited to infections requiring antibiotics, planned or emergent procedures, or addition of drugs known to interact with Celecoxib. The risk associated with Celecoxib will be explained to the subject in detail. A plan for dose interruption and reduction is included in the experimental plan. Subjects may withdraw from the trial at any time, or be withdrawn by the site PI for safety reasons at his/her discretion. The Data and Safety Monitor will review routine adverse events and trial results every six months, and serious adverse events within 72 hours. [name] will review urgent, persistent or life-threatening adverse events at all times during the trial. An on-call clinician at each site will be available for questions and consultation.

Due to the experimental use of celecoxib in LAM and TSC the trial has been designed with a focus on protecting subjects against risk from the medication including:

- 1- Small sample size consistent with the exploratory nature of the trial.
- 2- Specific exclusion criteria to prevent enrollment of subjects with significant co-morbidities that might place them at excess risk (see exclusion criteria)
- 3- Specific defined dose and holding criteria related to study adverse events.

VIII- Potential benefits

Participation in the proposed research will not guarantee direct benefit to participants, although it remains possible that a previously undiagnosed clinical abnormality will be brought to the clinician's attention. Information obtained from this research will provide information about the relationship between LAM treatment and patient outcomes. Sporadic LAM and Tuberous sclerosis affect more than 1.5 million people worldwide. Lung manifestations of TSC, including LAM are its most life threatening manifestations. Participants may also benefit from the effects of the drug in the trial, as well as frequent follow-up and monitoring. Information learned from this research may benefit women with LAM in the future. Understanding the interplay between mTOR dysregulation and COX 2 inhibition may have implications for patients suffering from other diseases as well.

IX-Data management

Data management overview

This study will use REDCap for electronic data capture. REDCap is a secure, web-based data management tool. Data will be entered into REDCap directly from the information collected on the source documents. All staff will be trained on REDCap. Training modules can be accessed via the website <https://redcap.partners.org/redcap>. Data entry into Redcap should be done within 5 business days from the time the information is collected.

Data Queries and Corrections

Data will be routinely reviewed for any missing data or discrepancies. Data discrepancies that are identified will be resolved within 5 business days. Each site must correct or update the database to resolve the data discrepancies.

Investigator Electronic Signature

The investigator or designee indicates their review of the data accuracy on all eCRFs pages for a subject with their e-signature within the REDCap system.

Maintaining the Clinical Center Subject File

Keep the following documents in the clinical center subject study file for each subject entered in the trial:

Copy of Confidential Subject Information page

Original signed consent form

Copies of all submitted source documents

Confidentiality Data Security Procedures and HIPAA considerations

All subjects must provide written informed consent and signed HIPAA authorization prior to the performance of any screening or main study procedures. Subject confidentiality will be protected throughout the study and no subject-identifying information will be released to anyone outside the project. Confidentiality will be secured through several mechanisms. Each subject will be assigned an anonymous study ID, which will be used on all study forms. Any study forms and paper records containing personal identifier information (e.g., address, phone number) will be kept secured and locked at each clinical site. No personal identifiers will be placed on biological samples and other documents forwarded to central labs and reading centers.

Access to all subject data and information at the clinical sites, including biological samples, will be restricted to authorized personnel. Only authorized personnel at the coordinating center will have access to study data files. Authorized personnel will be assigned user logon IDs, passwords and appropriate access privileges to study data. Study subjects will be identified only by their initials and subject ID number. No personal identifiers such as name, address, social security number will be entered into the study database. Any subject-specific data reported to any study committees will only be identified by subject ID number.

Finally, subjects will not be identified by name in any reports or publications, nor will the data be presented in such a way that the identity of individual subjects can be inferred. Analysis files created for further study by the scientific community will have no subject identifiers.

IX- Monitoring and Quality Assurance

a- Safety Monitoring

We will institute an independent Data Safety Monitoring Board to review procedures and adverse events that occur during the clinical study. Board members will not be involved in the active recruitment and daily routine of the study. The principal investigator will present study progress on a routine basis to the board members. Board members will review new cases and decide whether the study goals should be altered or the study should be stopped.

b- Monitoring of Subjects and Criteria for Withdrawal of Subjects

Subjects will be monitored throughout the clinical trial for new symptoms or complaints.

c- Outcome Monitoring

The clinical outcome of our participants will be continuously monitored by the study staff and the Data Safety Monitoring Board.

d- Adverse event reporting guidelines**Definitions**

Adverse event means any untoward or unfavorable medical occurrence in a human subject, including any abnormal sign (for example, abnormal physical exam or laboratory finding), symptom, or disease, temporally associated with the subject's participation in the research, whether or not considered related to the subject's participation in the research (modified from the definition of adverse events in the 1996 International Conference on Harmonization E-6 Guidelines for Good Clinical Practice).

Serious adverse event means any event temporally associated with the subject's participation in the research that meets any of the following criteria:

- Results in death
- Is life threatening (places the subject at immediate risk of death from the event as it occurred)
- Requires inpatient hospitalization or prolongation of existing hospitalization
- Results in a persistent or significant disability/incapacity
- Results in a congenital anomaly/birth defect or
- Any other adverse event that, based upon appropriate medical judgment, may jeopardize the subject's health and may require medical or surgical intervention to prevent one of the outcomes listed above.

Important medical events that may not result in death, be life-threatening, or require inpatient hospitalization may be considered an SAE when, based on appropriate medical judgment, they may jeopardize the subject and may require medical or surgical intervention to prevent one of the outcomes listed above.

An Unexpected Adverse Event is an adverse reaction, the nature or severity of which is not consistent with the applicable product information per the Investigator Brochure.

Life-threatening means that the subject was, in the view of the investigator, at immediate risk of death from the AE as it occurred. It does not include an AE that, had it occurred in a more severe form might have caused death.

Persistent or significant disability/incapacity means that the event resulted in permanent or significant and substantial disruption of the subject's ability to carry out normal life functions.

Associated with the use of the drug means there is reasonable possibility that the AE may have been caused by the drug.

Adverse event reporting

All AEs (serious and non-serious) will be recorded from start of study treatment (enrollment) through final study visit on the AE case report form.

All adverse events will be reported to the Partners Human Research Committee (PHRC) in accordance with the accepted guidelines. A 24-hour/7-day telephone number will be provided for contacting the licensed physician investigator for this purpose.

The research staff will monitor all subjects during their study involvement for evidence of any adverse events. Local study site personnel will report all serious adverse events (SAEs) to a designated medical monitor who will collect initial reports and oversee medical record retrieval for determination of final diagnosis.

Serious Adverse Events Reporting

All deaths and all SAEs require reporting from the start of treatment through 28 days after discontinuation of the study. The site is required to call the coordinating center to inform them of the SAE within the 24 hours of knowledge of the event. The site should also submit an SAE form via fax to the coordinating center and enter the SAE information onto the CRF within 24 hours of knowledge of the event.

An updated full written report will be filed as additional information becomes available within 10 working days (14 calendar days). The report will include a complete description of the event, use of all concomitant medications, and the local investigator's assessment of causality of the SAE. Non-serious adverse events will be reported at routine visits, documented on a separate adverse event form, and transmitted to the central coordinating center. All serious and unexpected adverse events will be reported to the overall study PI's.

Expedited Event Reporting

Adverse events that meet the definition of serious, study drug-related and unexpected (per the Investigator's Drug Brochure) qualify for expedited reporting to the regulatory authorities. The DSMB will perform a medical review of all deaths and study drug-related serious adverse events and evaluate for "unexpectedness".

The coordinating center will prepare Med Watch reports for those events identified as serious, study drug-related and unexpected as determined by the DSMB. The coordinating center will submit all unexpected study drug related SAEs as per 21 CFR 32.

Safety events requiring expedite reporting will be sent to the DSMB chair, with forwarding by the chair to the full board as needed, and DOD program office within 1-2 business days. DSMB chair will respond to the overall principal investigator and the coordinating center within 48 hours. Reporting framework and timelines are to be documented in Data and Safety Monitoring Plan after consultation with board members.

Coding for Adverse Events

All reported adverse events will be classified using the Common Terminology Criteria for Adverse Events (CTCAE), version 4.

X- References

Anonymous. (1991). "Lung function testing: selection of reference values and interpretative strategies. American Thoracic Society." Am Rev Respir Dis **144**(5): 1202-1218.

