a- Inclusion and exclusion criteria

We will perform a two-center phase I trial of celecoxib (COX-2 inhibitor) administered at 200mg by mouth daily for 6 months. The two centers are BWH and the National Institutes of Health Clinical Center. Up to 12 adult women with LAM will be recruited at both sites, and up to 8 subjects at BWH (between 4-8 at each site). The study will use the following eligibility criteria.

Inclusion criteria

- a. Female of age 18 to 69
- b. Ability to give informed consent
- c. Definite diagnosis of LAM

Typical cystic change on CT scan of the chest plus one of the following i) biopsy or cytology of any tissue demonstrating LAM, ii) angiomyolipoma, chylothorax, clinical or genetic diagnosis of tuberous sclerosis, iii) serum VEGF-D > 800pg/ml

- d. post-bronchodilator forced expiratory volume in one second \geq 70% of predicted and DLCO \geq 70% predicted during baseline visit.
- e. Women of childbearing potential must agree to use two forms of barrier contraception after screening visit, for the duration of study participation and for 30 days after last dose.

Exclusion criteria

- a. History of intolerance to non-steroidal anti-inflammatory drugs (NSAIDs)
- b. History of current regular use (daily most days of the week) of NSAIDs
- c. History of use of rapamycin or everolimus
- d. Uncontrolled intercurrent illness
- e. Pregnant, breast feeding or planning to become pregnant in the next 2 years
- f. Significant hematological (platelet count <100.000/ μ l or hepatic abnormalities (Liver function tests >2 times normal).
- g. Use of an investigational drug within 30 days of study start
- h. Inability to attend scheduled clinic visits
- i. Inability to give informed consent
- j. Inability to perform spirometry
- k. Creatinine > 1.0 mg/dl or eGFR < 60 ml/min
- l. Pneumothorax within past 8 weeks
- m. History of malignancy in the last 2 years other than basal cell skin cancer
- n. Use of estrogen containing medication within 30 days of enrolment
- o. Currently taking doxycycline, metformin, lupron or simvastatin

- p. Unable to undergo MRI
- q. History of seizure within the last year
- r. History of hepatitis or known active hepatitis B or C, or HIV positive serology
- s. Angiomyolipoma of diameter ≥ 4 cm
- t. History of vascular disease, including myocardial infarction or stroke
- u. History of ulcers or GI bleeding
- v. Allergy to sulfonamides, unless subject has previously used Celecoxib without any adverse reactions.

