The subject will be given the opportunity to take the consent home to consider participation. The subject will be asked to read the informed consent form prior to the physician or study coordinator asking the subject any questions concerning their health. Written, informed consent will be obtained after one of the investigators has reviewed the protocol verbally in detail with the subject. The physician will inform the subject that she has the alternative not to participate in the study. Subjects will receive a signed copy of the consent form for their records. After all questions are answered, and only after the consent form is signed by the patient and one of the MDs listed on the application will study screening commence. Subjects unable to give consent will not be approached.

Participation in other trials

Subjects will be allowed to participate in other research studies, as long as they do not involve the use of an investigational therapy.

Inclusion of Women and Minorities in this study

Adult women (>18 years of age) without any restrictions on age, race or ethnic group are eligible to participate in this trial. We will make every attempt to reach women of all ethnic groups, by advertising broadly through patient groups, LAM foundation and the internet.

V- Study procedures

Prior to enrolling in the study subjects must undergo the following tests to determine eligibility and baseline characteristics.

Screening and baseline testing		Timing prior to start of therapy
Informed consent	To be obtained before entry	
Medical history and physical examination	Including weight, height, SaO ₂ , vital signs (heart rate, blood pressure, temperature)	Within 28 days
Hematology	Complete blood count and differential (CBCD)	Within 28 days
Serum chemistries	Must include alkaline phosphatase, AST, ALT, bilirubin, serum creatinine, calcium and magnesium	Within 28 days
Urine test	Including pregnancy test	Within 28 days
Electrocardiogram (ECG)		Within 28 days
Pulmonary function test	Spirometry, Post Bronchodilator spirometry, TLC, DLCO	Within 28 days
Abdominal MRI		Within 3 months

Study Visit Summary

Study Procedures

All study procedures will be performed in accordance with accepted standards of practice. Relevant changes in clinical status and medication use, symptom history and adverse events will be reviewed at each study visit and in between study visit by a phone call placed from the research team to subjects enrolled in the study.

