Blood samples (chemistry, CBC) and biomarkers (VEGF-D, circulating TSC2 mutant cells) will be obtained via blood draws at indicated study visits. In addition, urine pregnancy testing will be performed at each study visit during the course of drug administration. Pulmonary function testing will be performed in accordance with ATS guidelines (Anonymous 1991) and according the schedule outlined in Table 1. Abdominal MRI will be performed at enrollment –if not done in the past 3 months-, and if angiomyolipoma or any other kidney abnormalities are detected, follow-up MRI will be performed at the discretion of the study team as indicated in Table 1. The St. Georges Respiratory Questionnaire (SGRQ) will also be administered and scored in accordance with published guidelines (Barr et al. 2000). Information on hospitalization and side effects will be obtained via direct subject interviews and medical record review.

Table 1: study visits and testing

Week

	Baseline	8	16	24
Visit number	1	2	3	4/early termination
Informed consent	X			
History and physical	X	X	X	X
Concurrent Medication Reconciliation	X	X	X	X
Adverse Event Review	X	X	X	X
Drug Administration Record	X	X	X	X
Liver, renal, glucose, cholesterol	X	X	X	X
EKG	X			
Urine pregnancy	X	X	X	X
CBC diff	X	X	X	X
MRI abdomen	X			X
Full PFT	X			X
St George's questionnaire	X			X
Stored serum and plasma	X	X	X	X
Exhaled breath condensate	X			X
measurement of TSC2 mutant cells	X			X

Study Windows

The screening to first dose period will be 28 days. All other study visit windows will be +/- one week.

Study visit procedures

Screening Visit (Visit 1)

The Screening Visit will take about 5 hours.

The following testing will be performed at the screening visit:

- Medical history
- Full physical exam
- Medication reconciliation
- Blood collection as outlined in table 1
- Urine pregnancy testing
- EKG
- MRI of the abdomen if not done in the last 3 months
- St. George's Respiratory Questionnaire (SGRQ)
- Spirometry, Post Bronchodilator spirometry, body plethysmography and diffusing capacity for carbon monoxide (DLCO)
- Stored blood for all exploratory endpoints
- Collection of exhaled breath condensates

Subjects who meet the inclusion criteria will be enrolled in the study and will start taking their medications

Visit 2

Visit 2 will take place 8 weeks after a subject starts taking study medication and will require about one hour.

The following testing will be obtained at this visit:

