We will perform assessments of clinical, functional and subject self-reported outcomes to assess potential benefit of celecoxib. Since lung function decline is a hallmark of LAM, we will perform spirometry, which will be interpreted in accordance with standard guidelines (Anonymous 1991). We will utilize the St. George's Respiratory Questionnaire (SGRQ) (Barr et al. 2000), as an assessment of the impact of treatment on dyspnea levels. Finally, we will record the incidence of hospitalization, complications from the disease, and other medical problems occurring during the study period

Stopping rules

The study will be monitored for the occurrence of a specified set of treatment related serious adverse events (TRSAE). The following two types of TRSAEs will be considered for early stopping of the study:

- Death considered to be probably or definitely related to Celecoxib

- Any grade IV toxicity considered to be probably or definitely related to Celecoxib

Subjects will be followed for 24 weeks while on therapy. During the 24 weeks of the trial, there will 4 study visits (screening visit and 3 visits while on therapy). Clinical and laboratory evaluations will be performed as outlined in Table 1.

Secondary outcome measurements

We will be performing several correlative studies as part of this protocol.

- a. VEGF-D levels. VEGF-D is well-known as a biomarker of LAM, and disease extent correlates with VEGF-D levels. Therefore we will measure VEGF-D prior to treatment and at serial time points during treatment. As this is a pilot study, formal statistical analysis is not planned.
- b. Circulating LAM cells. Circulating LAM cells may be isolated from peripheral blood of subjects on this trial, using density gradient and FACS methods. TSC2 mutations will be identified in these cells, if possible, and then the prevalence of LAM cells will be measured serially over time in subjects on this study. If no TSC2 mutation is identified, then mutations in other genes in this pathway (RHEB, MTOR) will be sought. However, we will not scan the entire genome in these analyses, but rather focus on just a few genes. We will test the number of circulating LAM cells over time to help assess whether the treatment, celecoxib, reduces the number of LAM cells.

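### When the first dose is delayed after Visit 1, pregnancy status can rest on a urine test up to 28 days old, because no repeat test is required

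*Combined protocol and SAP*

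**What the plan says.** **Before treatment.** The screening and baseline testing table in Section V lists a urine test, "Including pregnancy test", with a limit of 28 days before therapy starts. Study Windows sets the same limit: "The screening to first dose period will be 28 days". The Stopping rules subsection describes "4 study visits (screening visit and 3 visits while on therapy". The baseline column of Table 1 is Visit 1, which the visit descriptions call the Screening Visit. There is no separate visit on the day of first dose.

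**During treatment.** Study Procedures says that "urine pregnancy testing will be performed at each study visit during the course of drug administration". Section VII, under protection against general subject risks, likewise ties testing to study visits. On timing, "Visit 2 will take place 8 weeks after a subject starts taking study medication", and later visits have a window of one week either way.

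**Safeguards.** Exclusion criterion e in Section III-a rules out women who are "Pregnant, breast feeding or planning to become pregnant in the next 2 years". Inclusion criterion e says "Women of childbearing potential must agree to use two forms of barrier contraception after screening visit". Clinical status is also reviewed "in between study visit by a phone call placed from the research team".

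**The concern.** The protocol treats pregnancy as an exclusion and as a ground for discontinuation, and Section VII accepts that women of childbearing age must be enrolled in this disease. The intention is clearly that no pregnant woman starts celecoxib. For a woman who starts some days or weeks after Visit 1, nothing in the schedule checks this when exposure begins.

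Two kinds of pregnancy could pass unnoticed. One is a conception shortly before Visit 1, too recent for the urine test to detect; the barrier requirement begins only after screening and cannot prevent it. The other is a barrier failure between Visit 1 and the first dose.

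A delay is foreseeable. The protocol allows it, and eligibility depends on Visit 1 results that may not be ready the same day: liver and kidney chemistry, platelets, lung function, and abdominal MRI if there is no recent one. What is at stake is eligibility and participant safety, not the statistical results.

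**Working it through.** No power or sample-size formula applies. The check is a day count from the schedule.

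**Inputs from the protocol**
- Limit from screening (and its pregnancy test) to first dose: 28 days. It appears in both the screening table and Study Windows, and the two agree.
- Visit 2: 8 weeks = 56 days after first dose, with a window of 7 days either way.
- Pregnancy tests in Table 1: Visit 1 and weeks 8, 16 and 24.
- Planned enrolment: up to 12 women, aged 18 to 69.

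**Assumption, not in the documents:** a urine test turns positive about L = 14 days after conception (range 10 to 18).

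**Step 1. Age of the last test at first dose.** The plan allows 0 to 28 days. With a same-day test it is 0 days.

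**Step 2. Time on drug before the next test.** 56 − 7 = 49 days to 56 + 7 = 63 days. A first-dose test does not change this.

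**Step 3. Longest interval between consecutive tests.** Now: 28 + 49 = 77 days to 28 + 63 = 91 days. With the added test: 49 to 63 days. The 28 days removed are 28/91 = 31% to 28/77 = 36% of the interval. All of them fall before the first dose, so this is not a reduction in exposure to the drug.

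**Step 4. Conceptions that only the added test can find.** With a delay of d days, Visit 1 detects conceptions up to L days before Visit 1. A first-dose test detects those up to d − L days after Visit 1. The difference is a span of d days. For d = 28:

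| Assumed lag L | Days before Visit 1 | Days after Visit 1 |
|---|---|---|
| 10 | 10 | 28 − 10 = 18 |
| 14 | 14 | 28 − 14 = 14 |
| 18 | 18 | 28 − 18 = 10 |

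The days before Visit 1 precede the contraception requirement.

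**Step 5. Gestational age when the existing schedule would find such a pregnancy.** Dating gestation from 14 days before conception, the oldest pregnancy missed at Visit 1 would at Visit 2 be 14 + L + 28 + 63 days. For L = 14 this is 119 days = 17 weeks. For L = 18 it is 123 days = 17.6 weeks. Both are well short of the 30 weeks at which Section VII places the change from category C to category D.

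**The case against.** The strongest counter-argument is about weight. The only pregnancy harm the protocol describes occurs late, and Step 5 shows that the Visit 2 test would normally find a missed pregnancy long before then. The affected group may be empty: the Visit 1 description ends with eligible women being enrolled and starting medication, Table 1 already marks a drug record at that visit, and 28 days is a ceiling. An affected woman would have to be of childbearing potential, start late, and either have conceived just before Visit 1 without planning to, or have conceived afterwards despite two barrier methods. The shorter interval between tests does not shorten time on drug. Nor does a same-day test give certainty: under the same assumption, conceptions in the last 10 to 18 days before dosing would still be missed, as they are for women dosed on the day of Visit 1.

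All of this stands, and it keeps the point small. It does not remove the gap. Contraception, phone reviews and the exclusion criterion are not tests, and the exclusion is only as reliable as the test that enforces it. Pregnancy at any stage makes a woman ineligible, whatever the timing of the documented risk. The change brings delayed starters to the same standard as same-day starters and claims no more than that.

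**Conclusion.** The gap is real. Under the plan as written, a delayed starter can receive her first dose on a pregnancy test up to 28 days old, with 49 to 63 days on drug before the next scheduled test. At the longest delay, a first-dose test would detect a 28-day span of conceptions that Visit 1 could not, about 14 days of it (10 to 18) before contraception was required.

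This is a minor safety refinement, worth considering. The split around Visit 1 rests on the assumed detection lag; the 28-day limit and the day counts come directly from the protocol. The documents give neither the typical delay nor the number of women of childbearing potential, so the chance of an undetected pregnancy at first dose cannot be estimated. At most 12 women are involved, and probably fewer given the age range. Endpoints and analysis are unaffected.

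**What to change.** In the urine-test row of the screening and baseline table, and in Table 1, add one requirement: a woman of childbearing potential whose first dose is not on the day of Visit 1 must have a negative urine pregnancy test on the day of first dose, before dosing. A home kit is acceptable if the result is reported to the site and recorded, so no extra visit is needed. Leave the 28-day window for the other screening tests, the 8-week visit schedule and the contraception rules unchanged.

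The cost is at most 12 urine kits, one line in each of two tables, and a protocol amendment, which could be combined with the next one. The drawbacks are a slightly more complicated start for delayed starters and, with a home kit, reliance on a self-reported result.
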